5.3 Clinical/Laboratory Criteria (contd.)

- \_\_\_\_\_ k. No other prior malignancy is allowed except for the following: adequately treated basal cell or squamous cell skin cancer, in situ cervical cancer, adequately treated Stage I or II cancer from which the patient is currently in complete remission, or any other cancer from which the patient has been disease-free for 5 years.

5.4 Specimen Submission Criteria

- \_\_\_\_\_ a. Patients must be offered the opportunity to participate in specimen banking for future translational medicine studies (see [Section 15.0](#)).

5.5 Regulatory Criteria

- \_\_\_\_\_ a. All patients must be informed of the investigational nature of this study and must sign and give written informed consent in accordance with institutional and federal guidelines.
- \_\_\_\_\_ b. As a part of the OPEN registration process (see [Section 13.4](#) for OPEN access instructions) the treating institution's identity is provided in order to ensure that the current (within 365 days) date of institutional review board approval for this study has been entered in the system.

CLOSED EFFECTIVE 05/29/2014

## 6.0 STRATIFICATION FACTORS

Patients will be randomized using a dynamic balancing algorithm (15) with stratification based on:  
Prior systemic therapy for advanced or metastatic disease (none vs 1).

## 7.0 TREATMENT PLAN

For treatment or dose modification related questions, please contact [name] at [name] or [name], Jr. at [name]. For dosing principles or questions, please consult the SWOG Policy #38 "Dosing Principles for Patients on Clinical Trials" at <http://swog.org> (then click on "Policies and Manuals" under the "Visitors" menu and choose Policy #38)

### 7.1 Treatment Schedule

Patients will be randomized to either Arm 1: ARQ 197 or Arm 2: ARQ 197 and erlotinib.

#### a. Treatment schedule for Arm 1: ARQ 197

AGENT	DOSE	ROUTE	DAYS	INTERVAL	DURATION
ARQ 197*	360 mg (3 tablets) 720 mg total daily dose	By mouth	1-28	Twice daily (about 12 hours apart)	Until disease progression

#### b. Treatment schedule for Arm 2: ARQ 197+ erlotinib

AGENT	DOSE	ROUTE	DAYS	INTERVAL	DURATION
ARQ 197*	360 mg (3 tablets) 720 mg total daily dose	By mouth	1-28	Twice daily (about 12 hours apart)	Until disease progression
Erlotinib**	150 mg (1 tablet)	By mouth	1-28	Daily	Until disease progression

\* ARQ-197 is supplied as tablets for oral administration. Patients should take ARQ 197 twice daily (about 12 hours apart), with food.

\*\* Erlotinib tablets should be taken in the morning with up to 200 mL of water on an empty stomach (one hour before or two hours after eating).

NOTE: A cycle of therapy is defined as twenty-eight days. There will be no pause between cycles. Patients will be evaluated for response/progression every two treatment cycles and will continue on therapy until progression or other reason for removal from treatment (see [Section 7.6](#)).

### 7.2 Administration through G-tube

Administration of the study medications through a G-tube is not allowed.

### 7.3 Concomitant Medications

The use of supportive care medications is allowed according to institutional standards.

### 7.4 Drug Compliance

Drug compliance will be recorded by patients on the Intake Calendar (see [Appendix 18.2](#)). Institutional CRAs will review and ascertain patient adherence with protocol therapy at the end of treatment for each cycle. Calendar should be kept in the patient's clinic chart. Note that the Intake Calendar is provided only as a tool for tracking compliance. Sites may utilize institutional pill diaries or other source documentation in place of the Intake Calendar at the discretion of the treating physician.

### 7.5 Reporting Cycle-Specific Toxicity and Dose Information

Because this study contains an investigational drug for which CTEP holds the IND, it falls under CTEP requirement for full reporting. This involves required submission of cycle-specific toxicity and dose information (see [Section 14.4c](#), the **S1107** Treatment Form, and the **S1107** Adverse Event Form). A cycle is defined as 28 days.

### 7.6 Criteria for Removal from Protocol Treatment

- a. Progression of disease or symptomatic deterioration (as defined in [Section 10.2](#)).
- b. Unacceptable toxicity.
- c. All protocol treatment is held for any reason > 3 weeks.
- d. The patient may withdraw from the study at any time for any reason.
- e. Physician discretion.

### 7.7 Discontinuation of Treatment

All reasons for discontinuation of treatment must be documented in the Off Treatment Notice.

### 7.8 Follow Up Period

All patients will be followed for a maximum of three years.

## 8.0 DOSAGE MODIFICATIONS

### 8.1 NCI Common Terminology Criteria for Adverse Events

This study will utilize the CTCAE (NCI Common Terminology Criteria for Adverse Events) Version 4.0 for toxicity and Serious Adverse Event reporting. A copy of the CTCAE Version 4.0 can be downloaded from the CTEP home page (<http://ctep.cancer.gov>). All appropriate treatment areas should have access to a copy of the CTCAE Version 4.0.

### 8.2 General Considerations

- a. Missed doses are to be omitted rather than made up.
- b. If multiple toxicities are seen for any given single agent, administer dose based on greatest reduction required for any single toxicity observed.

- c. Reductions apply to the treatment given in the preceding cycle and are based on toxicities observed since the prior dose.
- d. Once dose is reduced, patients will continue at new dose. No dose re-escalations are allowed.
- e. If the patient vomits after taking the tablets, the dose is replaced only if the tablets can actually be seen and counted.
- f. Use of G-CSF and erythropoietin for patients being treated on this study is at the discretion of the treating physician. If used, it must be documented in the "Notes" section of the **S1107** Treatment Form.

### 8.3 Patient Evaluations

Patients will be evaluated every two weeks for the first eight weeks and then once every four weeks to determine toxicities and the appropriate dose modification (decrease, hold, or discontinue). If all protocol treatment is delayed more than three weeks, patients will be removed from protocol treatment.

### 8.4 Radiation Therapy for Palliation

If patients require radiation therapy for palliation in the absence of progressive disease please contact the primary Study Chair, [name] M.D. [contact] [name].

### 8.5 ARQ 197 Dose Modification

If ARQ 197 is held, erlotinib will also be held for patients on Arm 2 and resumed at the same time treatment with ARQ 197 is resumed. There will be no dose reduction of erlotinib if the toxicity was thought to be related to ARQ 197.

#### a. Hematologic toxicities:

Absolute neutrophil count (ANC) ( $\times 10^6/L$ )	Platelets ( $\times 10^6/L$ )	ARQ 197
$\geq 1,000$ and	$\geq 75,000$	100% dose
$< 1,000$ or	$< 75,000$	*Hold until ANC $\geq 1,000$ and platelets $\geq 75,000$ and reduce to the next lower dose level

\* Treatment may be held up to 21 days and can be resumed at the next lower dose level once ANC is  $\geq 1000 \times 10^6/L$  and platelet count is  $\geq 75,000 \times 10^6/L$ . Patients who cannot tolerate ARQ 197 at 120 mg BID will be removed from the protocol. No dose re-escalation is allowed.

CLOSED TO PUBLIC 05/29/2014

b. Non-hematologic toxicities:

The following modifications should be followed in the event of ARQ 197 related-non-hematologic toxicity.

Toxicity Grade(NCI CTCAE v4.0)	Percent of full dose of ARQ 197I
0-2	100%
3	Hold*
4	Hold*

\* Treatment may be held up to 21 days Any patient who experiences Grade 3 or greater non-hematologic toxicity which resolves to Grade 0 or 1 may be treated at a next lower dose level of ARQ 197 for subsequent doses. Patients who cannot tolerate ARQ 197 at 120 mg BID will be removed from the protocol. No dose re-escalation is allowed.

c. ARQ 197 Dose Level Reductions

Starting Dose	First Reduction	Second Reduction
360 mg BID	240 mg BID	120 mg BID

NOTE: Any patient who fails to tolerate treatment of 120 mg BID will be withdrawn from protocol treatment. If a treatment is delayed more than 21 days for the resolution of ARQ 197-related toxicities to Grade 0 or 1 patient will be removed from the protocol.

CLOSED EFFECTIVE 05/29/2014

8.6 Erlotinib Dose Modificationa

Toxicity (NCI CTCAE v4.0)	Dose Modification
Diarrhea	
Grade 1	None. Initiate therapy with loperamide.(8.7a)
Grade 2	Hold erlotinib. Initiate loperamide until resolution to Grade 0-1. Resume therapy at the same dose.
Grade 3 b or 4 b	Hold erlotinib. Initiate therapy with loperamide and appropriate supportive care until resolution to Grade 0 or 1 and then restart at 1 dose level lower
Rash	
Grade 1	None
Grade 2	None. Initiate treatment (8.7b) . If rash persists and is intolerable or worsens over 10 – 14 days, then reduce by 1 dose level.
Grade 3	Reduce by 1 dose level. If rash persists or worsens over 10 – 14 days, then interrupt erlotinib until resolution to Grade 0, 1 or 2 and then restart 1 dose level lower.
Grade 4	Permanently discontinue erlotinib.
Interstitial Lung Disease	
Any Grade	If ILD is suspected, erlotinib should be interrupted immediately pending diagnostic evaluation. If ILD is diagnosed, erlotinib should be discontinued permanently and appropriate treatment instituted as necessary.
Other Toxicities Attributable to Erlotinib	
Grade 1 or 2	None
Grade 3 or 4 b, c	Interrupt erlotinib until resolution to Grade 0 or 1 and then restart 1 dose level lower.
Other Toxicities (hematologic and non-hematologic) attributable to ARQ 197	
Grade 1 or 2	None
Grade 3 or 4	Hold erlotinib until ARQ 197 is resumed. If toxicity was deemed related to ARQ 197 no dose reduction of erlotinib is indicated

- (a) Doses that have been reduced should not be re-escalated. Any patient who fails to tolerate treatment at 50 mg/day will discontinue erlotinib and continue on single agent ARQ 197.
- (b) If the event does not resolve to Grade 0 or 1 within 21 days, erlotinib will be discontinued and patient will continue on a single agent ARQ 197
- (c) Only if  $\geq 2$  Grade level change from baseline

Erlotinib Dose Level Reductions

Starting Dose	First Reduction	Second Reduction
150 mg/day	100 mg/day	50 mg/day

NOTE: Any patient who fails to tolerate erlotinib at 50 mg/day will continue on single agent ARQ 197. If a treatment is delayed more than 21 days for the resolution of erlotinib-related toxicities to Grade 0 or 1, discontinue erlotinib and continue ARQ 197 alone.

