**Reported Adverse Events and Potential Risks:**

**Comprehensive Adverse Events and Potential Risks list (CAEPR) for OSI-774 (erlotinib, NSC 718781)**

The Comprehensive Adverse Event and Potential Risks list (CAEPR) provides a single list of reported and/or potential adverse events (AE) associated with an agent using a uniform presentation of events by body system. In addition to the comprehensive list, a subset, the Specific Protocol Exceptions to Expedited Reporting (SPEER), appears in a separate column and is identified with bold and italicized text. This subset of AEs (SPEER) is a list of events that are protocol specific exceptions to expedited reporting to NCI via CTEP-AERS (except as noted below). Refer to the 'CTEP, NCI Guidelines: Adverse Event Reporting Requirements'

[http://ctep.cancer.gov/protocolDevelopment/electronic\\_applications/docs/aeguidelines.pdf](http://ctep.cancer.gov/protocolDevelopment/electronic_applications/docs/aeguidelines.pdf) for further clarification. *Frequency is provided based on 3,622 patients.* Below is the CAEPR for OSI-774 (erlotinib).

**NOTE:** Report AEs on the SPEER **ONLY IF** they exceed the grade noted in parentheses next to the AE in the SPEER. If this CAEPR is part of a combination protocol using multiple investigational agents and has an AE listed on different SPEERs, use the lower of the grades to determine if expedited reporting is required.

CLOSED

Version 2.4, July 24, 2013

Adverse Events with Possible Relationship to OSI-774 (erlotinib) (CTCAE 4.0 Term) [n= 3622]			Specific Protocol Exceptions to Expedited Reporting (SPEER)  (formerly known as ASAEL)
Likely (>20%)	Less Likely (<=20%)	Rare but Serious (<3%)	
EYE DISORDERS			
	Conjunctivitis		Conjunctivitis (Gr 2)
	Dry eye		Dry eye (Gr 2)
	Eye disorders - Other (eyelash in-growth and/or thickening)		
		Eye disorders - Other (corneal perforation)	
		Keratitis	
GASTROINTESTINAL DISORDERS			
	Abdominal pain		Abdominal pain (Gr 3)
Diarrhea			Diarrhea (Gr 3)
	Dry mouth		Dry mouth (Gr 2)
	Dyspepsia		Dyspepsia (Gr 2)
	Gastrointestinal hemorrhage 		
		Gastrointestinal perforation 	
	Mucositis oral		Mucositis oral (Gr 3)
	Nausea		Nausea (Gr 3)
Vomiting			Vomiting (Gr 3)
GENERAL DISORDERS AND ADMINISTRATION SITE CONDITIONS			
Fatigue			Fatigue (Gr 3)
HEPATOBIILIARY DISORDERS			
		Hepatic failure	

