 Gastrointestinal perforation includes Colonic perforation, Duodenal perforation, Esophageal perforation, Gastric perforation, Ileal perforation, Jejunal perforation, Rectal perforation, and Small intestinal perforation under the GASTROINTESTINAL DISORDERS SOC.

 Includes infection of the skin (folliculitis or cellulitis) as complications of rash.

CLOSE

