**Warning:** Treatment with erlotinib should be used with extra caution in patients with total bilirubin > 3 x ULN. Patients with hepatic impairment (total bilirubin > ULN or Child-Pugh A, B and C) should be closely monitored during therapy with erlotinib. Erlotinib dosing should be interrupted or discontinued if changes in liver function are severe such as doubling of total bilirubin and/or tripling of transaminases in the setting of pretreatment values outside normal range.

**Warning:** Cases of hepatic failure and hepatorenal syndrome (including fatalities) have been reported during use of erlotinib, particularly in patients with baseline hepatic impairment. Therefore, periodic liver function testing (transaminases, bilirubin, and alkaline phosphatase) is recommended. In the setting of worsening liver function tests, dose interruption and/or dose

reduction with frequent liver function test monitoring should be considered. Erlotinib dosing should be interrupted or discontinued if total bilirubin is  $> 3 \times \text{ULN}$  and/or transaminases are  $> 5 \times \text{ULN}$  in the setting of normal pretreatment values.

**Warning:** Cases of hepatorenal syndrome, acute renal failure (including fatalities), and renal insufficiency have been reported. Some were secondary to baseline hepatic impairment while others were associated with severe dehydration due to diarrhea, vomiting, and/or anorexia or concurrent chemotherapy use. In the event of dehydration, particularly in patients with contributing risk factors for renal failure (e.g., pre-existing renal disease, medical conditions or medications that may lead to renal disease, or other predisposing conditions including advanced age), erlotinib therapy should be interrupted and appropriate measures should be taken to intensively rehydrate the patient. Periodic monitoring of renal function and serum electrolytes is recommended in patients at risk of dehydration.

**Gastrointestinal Perforation:** Patients receiving erlotinib are at increased risk of developing gastrointestinal perforation, which was observed uncommonly. Some cases had a fatal outcome. Patients receiving concomitant anti-angiogenic agents, corticosteroids, NSAIDs, and/or taxane based chemotherapy, or who have prior history of peptic ulceration or diverticular disease, are at increased risk. Erlotinib should be permanently discontinued in patients who develop gastrointestinal perforation.

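### Section 3.2b orders a permanent erlotinib stop after gastrointestinal perforation, but Section 8.6 has no perforation row, and its residual Grade 3-4 row can restart the drug

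*Combined protocol and SAP*

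**What the plan says.** **Section 3.2b (erlotinib, toxicology).** The paragraph on gastrointestinal perforation notes an increased risk that was uncommonly observed, adds "Some cases had a fatal outcome", and ends: "Erlotinib should be permanently discontinued in patients who develop gastrointestinal perforation". It sets no grade threshold and provides for no restart. The erlotinib adverse event list places the event in its rare-but-serious column, headed as below 3%. Footnote 3 defines the term: "Gastrointestinal perforation includes Colonic perforation, Duodenal perforation, Esophageal perforation, Gastric perforation, Ileal perforation, Jejunal perforation, Rectal perforation, and Small intestinal perforation".

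**Section 8.6 (erlotinib dose modification).** The table has rows for diarrhea, rash, interstitial lung disease (ILD), other toxicities attributable to erlotinib, and other toxicities attributable to ARQ 197. The Grade 3-4 instruction in the erlotinib residual row is: "Interrupt erlotinib until resolution to Grade 0 or 1 and then restart 1 dose level lower". Footnote (b) limits it: "If the event does not resolve to Grade 0 or 1 within 21 days, erlotinib will be discontinued". Footnote (c) requires a change of at least two grades from baseline. The dose levels are 150, 100 and 50 mg/day.

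**Elsewhere.** Section 8.7 gives management advice for diarrhea, skin toxicity and ocular disorders; the only perforation it names is corneal. Section 8.5 holds erlotinib when ARQ 197 is held and resumes both together. Section 7.6 permits removal from protocol treatment for unacceptable toxicity (b) or at the physician's discretion (e).

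**The concern.** A site deciding how to dose erlotinib after a toxicity will turn to Section 8.6, whose title covers exactly that. For gastrointestinal perforation the table leads to the residual row, and that row can end in a restart. The drug information section requires the drug to be stopped for good. Both instructions cannot be followed for the same patient.

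At stake is renewed exposure to erlotinib after an event that the protocol itself describes as sometimes fatal. The omission is easy to miss because Section 8 does carry over other material of this kind. Section 8.6 has permanent stops for diagnosed ILD and for Grade 4 rash, and Section 8.7 repeats the 3.2b advice on dehydration, bullous skin conditions and ocular disorders. A reader could reasonably take the table as complete.

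**Working it through.** The plan gives no figure on this point, so the check sets the two instructions side by side and traces one patient through the table.

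**1. Which row applies?** Perforation is not diarrhea, rash or ILD. The erlotinib adverse event list names it, with eight specific terms in footnote 3. The ARQ 197 list does not, either among possibly related events or among those with insufficient evidence. Attribution to erlotinib is therefore the expected reading, though not a certain one, and the residual erlotinib row applies.

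**2. Does footnote (c) block it?** The row needs a change of at least 2 grades.
- Grade 3 from baseline 0: 3 - 0 = 3. From baseline 1: 3 - 1 = 2.
- Grade 4 from baseline 0: 4 - 0 = 4. From baseline 1: 4 - 1 = 3.

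All are at least 2, so from a Grade 0 or 1 baseline the row applies.

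**3. Does footnote (b) block it?** Only if the event has not resolved to Grade 0-1 within 21 days. If it has resolved, the row's restart stands.

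**4. Resulting dose**

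| Dose at event | Section 8.6, resolved within 21 days | Share of 150 mg/day | Section 3.2b |
|---|---|---|---|
| 150 mg/day | 100 mg/day | 100/150 = 67% | 0 |
| 100 mg/day | 50 mg/day | 50/150 = 33% | 0 |
| 50 mg/day | no lower level | none | 0 |

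The conflict is confined to the first two lines. At 50 mg/day the restart cannot be carried out, and footnote (a) stops erlotinib in patients who fail to tolerate that dose.

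**5. Is the conflict reconciled anywhere?** Sections 7.6, 8.2, 8.3, 8.5 and 8.7 contain no rule on gastrointestinal perforation, no reference back to 3.2b and no order of precedence. The text of Section 8.8, listed in the contents as dose modification contacts, and the dosing policy cited in Section 7.0 were not available to check.

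**6. Do other 3.2b warnings conflict in the same way?** No. The hepatic rules also have no row in 8.6, but they are permissive: "Erlotinib dosing should be interrupted or discontinued if changes in liver function are severe". A hold followed by a restart can satisfy that. The dehydration, bullous and ocular warnings likewise allow interruption. Perforation is the only event for which 3.2b requires a permanent stop.

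**7. How often?** The only figure is the shared column heading of below 3%, which is not a perforation rate. Assuming the 78 planned patients split equally, Arm 2 has 78/2 = 39. The expected number with any perforation is then:
- at the 3% ceiling: 39 × 0.03 = 1.17;
- at an assumed 1%: 39 × 0.01 = 0.39;
- at an assumed 0.1%: 39 × 0.001 = 0.039.

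These count every perforation. The restart path also requires Grade 3-4, attribution to erlotinib, a dose of 150 or 100 mg/day, and resolution within 21 days. The documents give no proportion for any of these conditions, so the frequency of the path cannot be derived.

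**The case against.** The strongest reply is that the safeguard is already present. Section 3.2b belongs to the same protocol, names the event and the action, and attaches no condition of grade or attribution. A careful reader would apply a specific rule over a residual one. Section 7.6b and 7.6e permit removal. Perforation has no exception from expedited reporting in the erlotinib list, so a Grade 3 or 4 event must be reported, and Section 8.9 sends that report to the Study Chair. Section 8.3 requires toxicity review every two weeks for the first eight weeks, and Section 5.3i excludes active peptic ulcer disease. The document is also stamped closed effective 05/29/2014, which limits who can still be affected.

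Most of this stands. It shows that a restart in practice is unlikely and that the gap is one of harmonization. It does not remove the conflict: the removal criteria permit but do not compel, reporting does not set the dose, and nothing says which section prevails. As for the closed stamp, Revision #4 was still changing safety text in response to a request of April 2016, so a route for amendment existed after closure.

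Four stronger readings are tempting but not supported.
- A reader might infer that the protocol lacks a perforation rule, or that rechallenge was intended. The rule is in 3.2b, and nothing shows that a restart was chosen.
- A reader might extend the conflict to the Grade 1-2 row and to the ARQ 197-attributed rows, which on their wording also leave erlotinib in place. The CTCAE grade definitions are not in the documents, and attribution to ARQ 197 is unlikely, so these paths are not counted.
- A reader might turn the column heading into a probability: 1 - 0.97^39 = 0.70. That is the chance of at least one perforation of any kind at a ceiling that is not an event rate. It says nothing about restarts.
- A reader might infer from the footnotes when ARQ 197 may continue after a perforation. Footnote (b) continues it when the event has not resolved ("erlotinib will be discontinued and patient will continue on a single agent ARQ 197"), and footnote (a) has no resolution condition. Neither was written with perforation in mind.

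**Conclusion.** Sections 3.2b and 8.6 conflict for one defined path: an Arm 2 patient on 150 or 100 mg/day, baseline Grade 0-1, with a Grade 3-4 gastrointestinal perforation attributed to erlotinib that resolves to Grade 0-1 within 21 days. The table read literally gives 100 or 50 mg/day; Section 3.2b gives none.

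The conclusion rests on attribution to erlotinib, on a literal reading of the residual row, and on the absence of a precedence rule in the text available. The event is rare, the frequency of this path cannot be stated, and existing safeguards make an actual restart unlikely. The issue is patient safety in Arm 2. The primary endpoint, the two-stage rule and its error rates are not affected. It should be fixed because a stated dosing rule produces a result that the same protocol forbids, for an event that can be fatal.

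**What to change.** Add one row to the Section 8.6 table, modelled on the ILD row:

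> *Gastrointestinal perforation, any grade: permanently discontinue erlotinib (see Section 3.2b); this overrides the other rows of 8.6 and the resume-together sentence in 8.5.*

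The study team should decide separately, on clinical grounds, whether and when such a patient continues ARQ 197 alone, and should state the answer. It should not be presented as following from footnotes (a) and (b).

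The cost is one table row in an amendment, with no effect on sample size, schedule or analysis.

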**Comprehensive Adverse Events and Potential Risks list (CAEPR) for ARQ 197 (Tivantinib, NSC 750832)**

The Comprehensive Adverse Event and Potential Risks list (CAEPR) provides a single list of reported and/or potential adverse events (AE) associated with an agent using a uniform presentation of events by body system. In addition to the comprehensive list, a subset, the Specific Protocol Exceptions to Expedited Reporting (SPEER), appears in a separate column and is identified with bold and italicized text. This subset of AEs (SPEER) is a list of events that are protocol specific exceptions to expedited reporting to NCI via CTEP-AERS (except as noted below). Refer to the 'CTEP, NCI Guidelines: Adverse Event Reporting Requirements'

[http://ctep.cancer.gov/protocolDevelopment/electronic\\_applications/docs/aeguidelines.pdf](http://ctep.cancer.gov/protocolDevelopment/electronic_applications/docs/aeguidelines.pdf) for further clarification. *Frequency is provided based on 579 patients.* Below is the CAEPR for ARQ 197 (tivantinib).

**NOTE:** Report AEs on the SPEER **ONLY IF** they exceed the grade noted in parentheses next to the AE in the SPEER. If this CAEPR is part of a combination protocol using multiple investigational agents and has an AE listed on different SPEERs, use the lower of the grades to determine if expedited reporting is required.

CLOSED LIT

Version 2.2, February 19, 2016

Adverse Events with Possible Relationship to ARQ 197 (tivantinib) (CTCAE 4.0 Term) [n= 756]			Specific Protocol Exceptions to Expedited Reporting (SPEER)
Likely (>20%)	Less Likely (<=20%)	Rare but Serious (<3%)	
BLOOD AND LYMPHATIC SYSTEM DISORDERS			
	Anemia		Anemia (Gr 3)
CARDIAC DISORDERS			
	Sinus bradycardia		
GASTROINTESTINAL DISORDERS			
	Diarrhea		Diarrhea (Gr 2)
	Nausea		Nausea (Gr 2)
	Vomiting		Vomiting (Gr 2)
GENERAL DISORDERS AND ADMINISTRATION SITE CONDITIONS			
Fatigue			Fatigue (Gr 2)
INVESTIGATIONS			
	Lymphocyte count decreased		
	Neutrophil count decreased		Neutrophil count decreased (Gr 4)
	White blood cell decreased		
METABOLISM AND NUTRITION DISORDERS			
	Anorexia		Anorexia (Gr 2)
SKIN AND SUBCUTANEOUS TISSUE DISORDERS			
	Alopecia		
		Palmar-plantar erythrodysesthesia syndrome	
	Rash maculo-papular		Rash maculo-papular (Gr 2)

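### The hold triggers in Section 8.5 and the last row of Section 8.6 do not match, so an Arm 2 patient with Grade 3-4 ARQ 197-attributed anemia or lymphopenia can be given opposite erlotinib orders

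*Combined protocol and SAP*

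**What the plan says.** Three places in the protocol govern what happens to erlotinib when ARQ 197 causes a toxicity.

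- **8.5, opening sentence.** "If ARQ 197 is held, erlotinib will also be held for patients on Arm 2". Both drugs then restart together, and erlotinib is not reduced for a toxicity blamed on ARQ 197.
- **8.5a and 8.5b.** The hematologic table (8.5a) has two triggers, ANC below 1,000 and platelets below 75,000. With both counts at or above those limits it gives 100% dose. The hold is released on the same two counts: "Treatment may be held up to 21 days and can be resumed at the next lower dose level once ANC is" (the limits follow). The Grade 3-4 hold in 8.5b is limited by its own lead-in: "The following modifications should be followed in the event of ARQ 197 related-non-hematologic toxicity".
- **8.6, last row.** The row is headed "Other Toxicities (hematologic and non-hematologic) attributable to ARQ 197". It asks for no change at Grade 1 or 2. At Grade 3 or 4 it says "Hold erlotinib until ARQ 197 is resumed".

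The ARQ 197 risk list in 3.1b names four blood-count events as possibly related to the drug: anemia, "Lymphocyte count decreased", neutrophil count decreased and white blood cell decreased.

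**The concern.** Section 8.5a acts on two blood counts. The last row of 8.6 acts on CTCAE grade plus attribution and covers any hematologic toxicity. A Grade 3 or 4 hematologic event other than low ANC or platelets can therefore meet the 8.6 trigger without meeting any trigger in 8.5. Erlotinib is then held with a release condition tied to a drug that was never stopped.

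What is at stake is uniform delivery of Arm 2 treatment. Two sites following the same protocol could hold or continue erlotinib in identical patients. The frequency and extent of dose modifications by arm is a planned summary in 11.3, and it would mix the two practices.

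**Working it through.** No figure in the plan enters this point, so the check is a trace of the rules for one patient: Arm 2, Grade 3 or 4 anemia or lymphopenia attributed to ARQ 197, ANC at or above 1,000 and platelets at or above 75,000.

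**Step 1: is ARQ 197 held?**
- 8.5a: both counts are at or above the limits, so ARQ 197 is given at 100% dose. Hemoglobin, lymphocytes and white cells do not appear in the table.
- 8.5b: does not apply, because the event is hematologic.
- Result: no hold.

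**Step 2: is erlotinib held?**
- 8.6, last row, read literally: yes. The event is hematologic, attributed to ARQ 197, and Grade 3 or 4. Footnote (c), which requires a change of at least two grades from baseline, is not attached to this row.
- 8.5, opening sentence: no. Its condition, that ARQ 197 is held, is not met.
- Result: opposite orders.

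**Step 3: if erlotinib is held, what ends the hold?**

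| Clause | What it provides | Does it restart erlotinib here? |
|---|---|---|
| 8.6, last row | Release when ARQ 197 resumes | No; ARQ 197 was not stopped |
| 8.6, footnote (b): "If the event does not resolve to Grade 0 or 1 within 21 days, erlotinib will be discontinued" | Discontinuation after 21 days | No; it is marked on the diarrhea row and the erlotinib-attributed row only |
| 8.6, NOTE | Discontinuation for erlotinib-related delay or intolerance | No; the event is attributed to ARQ 197 |
| 8.5c, NOTE: "If a treatment is delayed more than 21 days for the resolution of ARQ 197-related toxicities to Grade 0 or 1" | Removal from the protocol | No; if an erlotinib hold counts as a delay, the outcome is removal |
| 7.6c and 8.3 | Removal when all treatment is held or delayed more than three weeks | No; ARQ 197 continues |

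One patient can thus be given an erlotinib hold without end, removal after 21 days, or uninterrupted erlotinib, depending on which clause the site reads first.

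**Step 4: is the event foreseeable?** Of the four hematologic terms listed as possibly related in 3.1b, only neutrophils have a trigger in 8.5a. The other three (4 - 1 = 3) do not. Eligibility criterion 5.3c sets minimum values for WBC, ANC and platelets, but none for hemoglobin or lymphocytes. A CBC with differential is on the calendar at every on-treatment toxicity visit, so such events would be detected.

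**Step 5: the general mismatch.** If a count below an 8.5a limit is Grade 1 or 2 by CTCAE and is attributed to ARQ 197, 8.5 holds both drugs, while the 8.6 row asks for no erlotinib change. No passage says which governs. Whether a given count falls in this zone depends on CTCAE v4.0 grade limits, which the protocol does not reproduce.

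**The case against.** The strongest reply is that the 8.6 row only restates the opening of 8.5. Both say that erlotinib waits for ARQ 197 and is not reduced, and a hold that lasts until ARQ 197 resumes presupposes that ARQ 197 was stopped. On that reading, no ARQ 197 hold means no erlotinib hold, and the gap disappears. This is a plausible account of the intent. But the row's trigger is grade and attribution, with hematologic events named and no condition that ARQ 197 be held. The lenient reading therefore gives the opposite order to the row's literal text, so it shows the conflict without removing it.

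Unacceptable toxicity (7.6b) and physician discretion (7.6e) allow removal from treatment, and Section 7.0 refers sites to contacts for dose questions. These help in single cases but define no restart.

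Four stronger readings are tempting, and the documents do not support them:
- **That ARQ 197 at full dose during severe anemia is itself an error.** Whether anemia or lymphopenia should have its own row is a clinical choice; the documents do not contradict themselves on that.
- **That the combination response rate is distorted because an affected patient in effect receives ARQ 197 alone.** Elsewhere, 8.6 deliberately moves Arm 2 patients to single-agent ARQ 197, so this is not peculiar to the gap.
- **That a definite platelet range receives conflicting orders.** That needs grade limits from outside the documents. It also needs attribution to ARQ 197, and 3.1b lists platelet decrease among events with insufficient evidence of causation.
- **That the number of patients can be estimated.** The risk list's band of at most 20% carries no grade, so applying it to 35 patients does not give a Grade 3-4 count.

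**Conclusion.** Wrong as written: an internal contradiction between 8.5 and the last row of 8.6. It holds for Arm 2 patients with a Grade 3-4 hematologic toxicity attributed to ARQ 197, other than low ANC or platelets, while both counts stay at or above the 8.5a limits. If either count falls below its limit, ARQ 197 is held and a restart point exists.

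A reader might infer that erlotinib is certain to stop for good in these patients. The documents do not establish that; they support that order, its opposite, and possibly removal. The number of patients affected is unknown, because no Grade 3-4 rate is given. The primary-endpoint design figures (35 eligible patients per arm, 2% significance level, 87% power) do not depend on this point. It should be corrected because it touches treatment delivery and safety, but it does not threaten the primary analysis.

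**What to change.** The sponsor should reconcile the opening sentence of 8.5, tables 8.5a and 8.5b, and the last row of 8.6, so that:

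1. the triggers for holding ARQ 197 and for holding erlotinib because of ARQ 197 toxicity agree;
2. the text states which governs erlotinib when a blood count and a CTCAE grade point different ways;
3. every hold has a stated end.

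Which clinical rule to adopt is the sponsor's decision. The cost is table wording in one amendment. No new assessments are needed, since the blood counts are already collected at each on-treatment toxicity visit.
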